16.7.2 Medtronic Records

Medtronic will maintain the following records for each site:

- All related essential correspondence that pertains to the site
- Fully executed CTA

- All Ethics Board approval or determination (Ethics Board waiver) documentation
- All approved CIP versions
- All approved DRF, ICF and Authorization forms (authorization forms in applicable geographies)
- All reported data including CRFs, images, device data obtained via remote transmission or device uploads for applicable products, medical information received to support adjudication of adverse events and deaths.
- Training, compensation, monitoring records

Other records required per local regulations will be maintained.

16.8. Reporting Requirements

16.8.1. Site Reports

The site is responsible for the preparation and submission of the reports to Medtronic and/or the Ethics Board cited in Table 3. In addition, if an Ethics Board takes any action with respect to PSR pertinent documentation it must be forwarded to Medtronic. Sites are responsible to submit reports per applicable regulations to all required parties.

Table 3: Site Reports

Report	Submit To	Description
Withdrawal of Ethics Board approval	Medtronic	Notification within five working days
Other actions by Ethics Board	Medtronic	Any actions taken by the Ethics Board that affects any aspect of the PSR conduct must be submitted to Medtronic as soon as possible.
Deaths	Medtronic Ethics Board (as required)	The site must submit notification of all deaths to Medtronic and licensing authority, if applicable per local law, upon site's first awareness. The site must also report to their Ethics Board per their requirements/local law.
Adverse Events	Medtronic Ethics Board (as required)	The site must submit all Adverse Events (device, procedure-related and therapy-relevant) to Medtronic and licensing authority, if applicable per local law, upon site's first awareness. The site must also report to their Ethics Board per their requirements/local law.

Report	Submit To	Description
Deviation	Medtronic Ethics Board (as required)	Deviations should be reported to Medtronic and to Ethics Boards, competent authorities or other regulatory bodies per their requirements and/or local law.

16.8.2. Medtronic Reports

Medtronic will complete reports per product-specific requirements, as shown in Table 4. Medtronic will comply to any local reporting requirements, if applicable. Medtronic may also provide participating sites with periodic reports that will present both site PSR status and aggregate information. In addition, participating sites will have access to their own registry data for ad hoc reporting.

Table 4: Medtronic Reports

Report	Submit to	Description
Progress Report	Regulatory Authority	Progress reports will be submitted to regulatory authority as required, and to PI & Ethics Boards as requested.
Adverse Events	Regulatory Authority Ethics Board	Summary of reportable Events will be provided to Regulatory Authorities per their requirements, (any negative trends will be reported to participating clinicians as appropriate). Summary of reportable Events may be provided to other applicable parties as required per local regulations.
Withdrawal of Ethics Board approval	Participating Sites Regulatory Authority	Notification within five working days after the sponsor first learns of the withdrawal of approval. To be reported to Regulatory Authorities as required.
Withdrawal of regulatory approval, if applicable	Participating Sites Ethics Board	Notification within five working days after sponsor first learns of the withdrawal of approval. To be reported to Regulatory Authorities as required.

16.9. Publication and Use of Information

Sites may publish the results of and information from their PSR collected data provided the publication is made in accordance with the terms and conditions of the agreement between the site and Medtronic. Publications utilizing PSR data will be processed in accordance with Medtronic Standard Operating Procedures and Policies. A publication strategy designed to provide direction and support in the development of clinical publications may be utilized. The strategy will outline the number of committees, membership criteria, authorship criteria, criteria for developing manuscripts, abstracts and public presentations, publication approval and publication timelines.

16.9.1. Publication Committees

The PSR may have multiple Publication Committees to align with numerous therapies or products supported by the PSR. Medtronic will assess recommendations put forth by the committees and will review and comment on publications. Committees may be at a therapy or product level as warranted by the intended use of the data. Members may include, but are not limited to, participating clinicians, team members, and Medtronic representatives including research scientists, statisticians, and others as applicable.

The Publication Committees are responsible for the following:

Medtronic Business Restricted

- Overseeing the development of manuscripts and abstracts
- Reviewing, approving and prioritizing publications
- Providing input on the scientific merit and clinical relevance of publications
- Applying and enforcing the authorship guidelines set forth in the publication strategy

Publication Committee membership does not automatically qualify a member for authorship.

16.9.2. Criteria for Determining Authorship

Authorship for manuscripts will follow the *Uniform Requirements for Manuscripts Submitted to Biomedical Journals*, ICMJE guidelines (www.icmje.org) and be based on the following criteria:

- Substantial contributions to the conception or design of the work; or the acquisition, analysis or interpretation of data for the work; AND
- Drafting the work or revising it critically for important intellectual content; AND
- Final approval of the version to be published; AND
- Agreement to be accountable for all aspects of the work in ensuring that questions related to the accuracy or integrity of any part of the work are appropriately investigated and resolved.

In addition, the following should be implemented:

- First author and all subsequent authorship will be determined by contribution to each of the above criteria. All authors must sign the manuscript that will be submitted.
- A minimum of verbal approval prior to submission is the minimum required for an abstract.
- All clinicians not listed as co-authors will be acknowledged and will be individually listed in an appendix as permitted by the scientific journal.
- Medical writer support must be disclosed either by inclusion of the medical writer as an author or in the Acknowledgements, depending on the contribution.

16.9.3. Publication Requests

Publication requests will be evaluated for scientific validity and the ability of Medtronic to provide resources. They will be approved by the responsible Publication Committee which will need to ensure that requests do not present conflicts with other geographical regions. If multiple geographies contribute data, co-authorship will be determined using the guidelines for authorship selection described above.

16.9.4. Publication of Results

A description of the clinical registry shall be registered in a publicly accessible database. Results will be made publicly available.

16.10. Suspension or Early Termination

Suspension is a temporary postponement of PSR activities relating to enrollment at a site or at a registry level. Termination is the termination of site PSR activities at a site or at a registry level.

16.10.1. Criteria for Suspension or Early Termination

Reasons for suspension or termination of a site may include but is not limited to:

- Ethics Board approval expiration
- Consistent non-compliance to the CIP (e.g., failure to follow patients, etc.)
- Lack of enrollment
- Non-compliance to regulations and the terms of the CTA with Medtronic
- Ethics Board suspension of the site

Considerations related to PSR suspension and termination include but is not limited to:

- If Medtronic suspends or terminates the PSR, Medtronic will promptly inform the site of the suspension/termination along with the reason and inform regulatory authorities, where required.
- If Medtronic suspends or terminates the PSR, the site must inform the patients, where required.
- In the case of PSR suspension or termination, for reasons other than a temporary Ethics Board approval lapse, the site will promptly inform the Ethics Board, if applicable

If the site suspends or terminates participation without prior agreement of Medtronic:

- The site must promptly inform Medtronic and provide a detailed written explanation of the termination or suspension
- The site must promptly inform the institution (where required per regulatory requirements)
- The site must promptly inform the Ethics Board, if applicable
- The site must inform the patients, where required.

If the Ethics Board suspends or terminates its approval:

- The site must promptly inform Medtronic and provide a detailed written explanation of the termination or suspension within five business days
- Patient enrollment must stop until the Ethics Board suspension is lifted
- Patients already enrolled should continue to be followed in accordance with the Ethics Board policy or its determination that an overriding safety concern or ethical issue is involved
- The site must inform his/her institution (where required per local requirements)
- The site must promptly inform the patients, where required.

17. References

Recommendations from the Heart Rhythm Society Task Force on Device Performance Policies and Guidelines, Heart Rhythm, Volume 3, No. 10, October 2006

Gliklich RE, Dreyer NA: Registries for Evaluating Patient Outcomes: A User's Guide. 2nd Edition. AHRQ publication No. 13-EHC111. April 2014

18. Appendices

Surgical Condition/Therapy Appendix

19. Version History

Version history is maintained within a separate document.

Condition/Therapy Appendix: Surgical

A. Surgical and Medical Procedure Background

The Product Surveillance Registry (PSR) supports a wide range of surgical and medical procedures completed using one or more Medtronic products in open, minimally invasive, robotic, endoscopic, and percutaneous procedures.

Often classified as the 'traditional type' of surgery, open surgery occurs when incisions are made in a patient through which surgeons insert various instruments to conduct the surgery.

Minimally invasive surgery (MIS) is a technique where operations are performed through small incisions in the body whereby surgical instrumentation are inserted allowing the procedure to be performed with minimal tissue interruption (e.g. laparoscopic surgery).

Robot-assisted laparoscopic surgery utilizes a Robotic Assisted Surgical Device (RASD) to provide three-dimensional visualization and articulation of the robotic instrument wrists.

Additionally, endoscopic and percutaneous surgical procedures offer additional options to perform MIS. Endoscopic surgeries involve the insertion of a long, thin tube, typically with the use of a camera and light, directly into the body to perform a surgical procedure.

Percutaneous surgery is characterized by being done through one or more small puncture sites or minor incisions through the skin, often without direct visualization of the underlying anatomy.

Details on each of the market approved study devices (including e.g. device description, contraindications and potential complications) are included in the current applicable version of the Instructions for Use document.

B. Data Collection

Steps to minimize bias in the PSR Surgical patient population align with Section 6.3 (Steps Taken to Minimize Bias). These steps are followed to ensure enrollments are an appropriate representation of the patient population. Product specific known or foreseeable factors available in product labeling/IFU may be taken into consideration. Medtronic may limit enrollment using an Enrollment Guide to account for specific cohorts of product use and ensure adequate enrollments to effectively assess study objectives.

B.1 Enrollment

Patients may be enrolled prior to or after the surgical or medical procedure. Whether a particular cohort under this CIP enrolls patients before or after surgery or both, is defined in the applicable analysis plan or addendum. The site will make every attempt to approach all eligible patients for enrollment and

Medtronic Business Restricted

perform a thorough review of the patient's medical record to ensure requested baseline and medical history information is complete. When enrolling a patient before surgery, procedures are recommended to occur within 30 days of consent. When enrolling a patient after surgery, it is recommended to do so within 30 days following the procedure. If deemed necessary, the study team is allowed to deviate from those 30 days before or following surgery, provided justification in the applicable analysis plan or addendum.

If the patient is enrolled into the registry prior to the surgical or medical procedure but the procedure is not completed with an eligible product, the patient will be exited from the registry. The data that is to be collected on patients exited early will include the Enrollment CRF and the Exit CRF at minimum. Other CRFs, if collected, will be defined in the applicable analysis plan or addendum. No data will be collected after the patient is exited. Vulnerable patient populations such as pediatric patients may be enrolled when the use of the device is approved in the population and region per the applicable instructions for use (IFU). Regional requirements will be followed and described in the applicable analysis plan or addendum.

Sites may submit to their Ethics Board for a full waiver of consent if applicable. Patients at sites where the Ethics Board *has not* granted a full waiver of consent are considered enrolled once informed consent has been obtained. Patients at sites where the Ethics Board *has* granted a full waiver of consent are considered enrolled once the patient's eligibility is assessed and verified and the Enrollment CRF is complete. Relevant enrollment data collected for eligible patients include but are not limited to:

- Eligibility verification (i.e. Section 8.3 Inclusion Criteria and Section 8.4 Exclusion Criteria).

Study activities (e.g., data collection and entry) can only start after the patient is enrolled in the study.

B.2 Baseline

The following types of data may be collected at baseline for enrolled patients regardless of procedure performed:

- Demographics
- Medical History
- Surgical History
- Vital signs
- Quality of Life or satisfaction measurements, if applicable

B.3 Procedure

The following types of data may be collected for enrolled patients as applicable for the procedure performed:

- Perioperative details
- Device details
- Adverse Events, Device Deficiencies, Deaths, and deviations are to be reported to Medtronic upon awareness
- Imaging, if applicable
- Procedure recordings, if applicable
- Quality of Life or satisfaction measurements, if applicable

[figure not shown]
[figure not shown]
B.4 Follow-up Reporting Frequency & Data Collection

Patients will be treated in accordance with the routine clinical practices of their respective care provider. However, in 'real world' clinical practice, the frequency of in-person follow-up visits may vary for many reasons (e.g., patient's personal circumstances, condition, physician preference, etc.) resulting in more or fewer in-person visits.

As a result, the PSR is based on an active surveillance model which requires sites to complete a patient status assessment post-procedure, regardless of whether the patient is seen in-person per the physician's routine follow-up care practices. This approach ensures a robust dataset while increasing the continual awareness of patient status throughout their registry participation.

Data will be captured through 30 days post-procedure (to be reported between day 30 and 37) at a minimum and may be captured up to 60 months (or 5 years) post-procedure (Figure 1).

For procedures requiring long-term follow-up data, assessments will be collected at least annually with a maximum follow-up duration of 60 months at which time the patient will be exited (Figure 1). The total duration of follow-up for products requiring long-term follow-up data collection will be determined by various factors including but not limited to product lifecycle, recurrence rate, or regulatory requirements. The timing of the patient assessments and exit will be outlined in the corresponding Analysis Plan or Addendum. Refer to Figure 2 for an example of a long-term follow-up data collection schedule.

Surgical Appendix - Figure 1: Follow-up Schedules**Surgical Appendix - Figure 2: Example of a Long-term Schedule**

Follow-up data will be collected for enrolled patients and may include, but are not limited to:

- Patient status
- Readmissions
- Imaging information, if applicable
- Procedure recordings, if applicable
- Quality of Life or satisfaction measurements, if applicable
- Adverse Events, Device Deficiencies, Deaths, reinterventions, and deviations are to be reported to Medtronic upon awareness

B.5 Events

All procedure or device related events are to be reported upon site awareness. Submit any additional supporting evidence which could assist in the assessment and review. Further supporting evidence not originally provided by the site may be requested by Medtronic to aid in the adjudication of the event.

Refer to Table 1 below for Unavoidable Adverse Events, which if resolved within the timeframe specified, are **not** required to be reported.

Surgical Appendix - Table 1: Unavoidable Adverse Events

Event Description	Time Frame (hours) from end of Procedure
Anesthesia related nausea / vomiting/ headache	24 hours
Low-grade fever (<100°F or < 37.8°C)	48 hours
Pain at Access Site	72 hours
Mild to moderate bruising / ecchymosis at access site	168 hours (7 days)
Back pain related to lying on the table	72 hours
Constipation	72 hours
Postoperative pain and/or complications that the Investigator considers common and within normal limits for the procedure and its related medication.	

Refer to Table 2 below, for a listing of potential **reportable** Adverse Events. The listing is provided to facilitate more complete and consistent reporting and is not intended to be a comprehensive listing of all reportable events.

Patients with adverse events that have not resolved at the time of the final registry timepoint will be followed until resolution, for up to 30 days after the final registry timepoint, or other applicable period as defined in the analysis plan or addendum.

Surgical Appendix - Table 2: Potential Reportable Adverse Events

Allergic reactions	Inflammatory reaction	Seroma
Bleeding/hematoma	Inadvertent injuries to other tissues or organs	Thromboembolic complications
Blood transfusion	Nerve damage	Vascular injury
Cardiopulmonary complications	Nerve entrapment	Visceral adhesions
Chronic pain	Hernia Recurrence	Visceral injuries
Damage to pericardium	Renal failure	Wound dehiscence
Infection	Respiratory complications	

The site will report the clinician's assessment of an adverse event relative to relatedness (e.g., device or procedure), seriousness and severity. The definitions for seriousness and relatedness can be found in section 12.1, Table 2: Adverse Event and Device Deficiency Definitions. The definitions for severity are in Table 3 below.

Surgical Appendix - Table 3: Definitions for Event Severity

Event type	Severity Definition
Mild event	Signs, or symptoms that are easily tolerated by the subject, or are clinical or diagnostic observations of the investigator.
Moderate event	Signs, or symptoms that cause discomfort and interfere with normal functioning. Local or non-invasive intervention may be indicated.
Severe event	Signs, or symptoms that disable the subject, are medically significant, lead to hospitalization or prolongation of hospitalization.

B.6 Lost to Follow-up

Follow-up data may be collected via medical record review within the expected reporting period. In cases where a subject interaction is required for a study endpoint, subjects may be considered lost to follow-up if at least two attempts to contact the subject are unsuccessful. The method of attempt (e.g., one letter and one phone record, or two letters) must be documented in the subject's source documentation. In addition, regulation set forth by the governing EC/IRB must be followed.

B.7 Exit

Enrolled patients will be exited from the registry once the applicable duration of follow-up has been completed unless exited early for unavoidable reasons. Patients with an ongoing reportable Adverse Event or Device Deficiency at the time of final registry timepoint will be followed until resolution for up to 30 days after the final registry timepoint, or other applicable period as defined in the analysis plan or addendum.

B.8 Schedule of Data Collection

Surgical Appendix - Table 4: Data Collection Schedule

	Enrollment and Baseline	Procedure	Follow-up Assessment
Informed Consent, if applicable	X		
Patient status		X	X
Demographics and Medical and Surgical History	X		
Vital signs	X	X	X
Procedure information		X	
Imaging, if applicable	X	X	X
Product and/or therapy information, if applicable	X	X	X
Quality of Life or satisfaction measurements, if applicable	X	X	X
Readmission			X
Reintervention		Reported upon site awareness	
Procedure/Device Related Adverse Events		Reported upon site awareness	
Device Deficiencies		Reported upon site awareness	
Deaths		Reported upon site awareness	
Deviations	Reported upon site awareness		

C. Data Collection Details

Data collection details and CRFs (where required) are provided under separate cover.

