8.3. Inclusion Criteria

- Patient or legally authorized representative (LAR) provides authorization and/or consent per institution and geographical requirements
- Patient has, or is intended to receive or be treated with, an eligible Medtronic product (Section 4.3)
- Patient is consented within the enrollment window of the therapy received, as applicable

Additional criteria may be required, refer to Condition/Therapy Appendix for further guidance.

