## 5.3 Study Population

Subjects treated with an eligible Medtronic market released surgical product(s) and enrolled within the enrollment window are eligible to participate in the PSR with additional inclusion/exclusion criteria listed below. Not all Medtronic market released surgical products are required to be included into the PSR Surgical platform. Product eligibility is based on the determination that there is an interest or requirement for obtaining additional information to further characterize product performance following market release.

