### 7.1 Study Subjects

#### 7.1.1 Disposition of Subjects

A subject is enrolled in the study when he/she signs and dates the Informed Consent, unless a full waiver of consent has been approved by the site's IRB or EC, meets all the inclusion/exclusion criteria, and is treated with at least one eligible Medtronic market released surgical product. A flow chart, tables, and/or listings may be used to summarize subjects' disposition.

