#### 7.1.3 Analysis Sets

Subjects included in any analysis sets must consent to the PSR, unless a full waiver of consent has been approved by the site's IRB or EC, and meet all the inclusion/exclusion criteria. They must have been treated with at least one Medtronic market released surgical product. Additional inclusion/exclusion criteria include, but are not limited to specific components or models, time frame, data cutoff date and geography. For details, please refer to Analysis Plan (AP) or Addendum (AD).

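### Where patients consent after the procedure, deaths before consent are in effect not counted, so early mortality reads low; the SAP neither labels nor splits it and claims worldwide representativeness without limit

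*Protocol*

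**What the plan says.** **Enrolment route.** Surgical Appendix B.1 allows enrolment before or after the procedure. For the second route, "When enrolling a patient after surgery, it is recommended to do so within 30 days following the procedure"; an Analysis Plan (AP) or Addendum (AD) may depart from the 30 days with justification. The route is set cohort by cohort: "Whether a particular cohort under this CIP enrolls patients before or after surgery or both, is defined in the applicable analysis plan or addendum".

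**When a patient counts as enrolled.** B.1 says that patients at sites whose Ethics Board has *not* "granted a full waiver of consent are considered enrolled once informed consent has been obtained" (the negative comes just before the quoted words). At full-waiver sites enrolment follows the eligibility check and completion of the enrolment form. B.1 adds: "Study activities (e.g., data collection and entry) can only start after the patient is enrolled in the study".

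**Who is analysed.** SAP 7.1.1: "A subject is enrolled in the study when he/she signs and dates the Informed Consent, unless a full waiver of consent has been approved". SAP 7.1.3: "Subjects included in any analysis sets must consent to the PSR, unless a full waiver of consent has been approved". SAP 7.9.1.3 evaluates events among subjects who are enrolled, eligible and operated on.

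**What is estimated.** SAP 4.2 lists mortality as a secondary outcome without a performance goal; for long-term products, survival analyses are optional. SAP 7.9.2 says only that mortality is to be computed and that survival outcomes use Kaplan-Meier. It gives no time origin, no rule for patients who enter late and no summary by enrolment route. SAP 7.9.1.2 assesses the short-term event rate after the procedure or within 30 days of it.

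**What is claimed.** SAP 6.2 says without qualification that the registry sample represents the population worldwide.

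**The concern.** The recommended window for consent after surgery is as long as the short-term endpoint period, so a patient can die inside that period before there is any chance to enrol. At a site that needs consent, such a patient has no data collected and cannot enter an analysis set. The remaining patients were all alive at consent, yet their mortality would be read as mortality after the procedure.

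At stake is a listed safety outcome of a surveillance registry. An unlabelled figure would understate early deaths by an amount that depends on how many patients came in after surgery and how late they consented. Two reports with different mixes of route could then differ for that reason alone. The SAP 6.2 statement would carry the understated figure to patients who were never sampled.

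**Working it through.** **1. The plan's own figures.** SAP 6.1 uses N = 1.96² × p(1 − p) / halfwidth². For p = 10% and halfwidth 5% this is 138.3, rounded up to 139; for p = 20% and 5% it is 245.9, rounded up to 246. All nine cells of the table reproduce. They are not in dispute; N = 139 and N = 246 (the largest) serve below as realistic sizes.

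**2. Inputs for the bias.** The documents give no mortality, death timing, consent timing or mix of routes, so all of these are assumed:
- D, the true 30-day mortality: 0.5%, 2% or 5%.
- f, the share enrolled by consent after the procedure: 1 or 0.5.
- Consent day uniform on (0, L), with L = 30 (the recommended window) or L = 7, independent of death.
- F(t), the distribution of death times over days 0 to 30: even, or front-loaded (exponential, mean 10 days, truncated at 30).
- Deaths before consent are never enrolled; all survivors are.

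**3. Share of deaths missed**, m = (1/L) ∫₀ᴸ F(t) dt.
- Even: m = L/60, which is 0.500 for L = 30 and 0.117 for L = 7.
- Front-loaded: m = [1 − (10/L)(1 − e^(−L/10))] / (1 − e^(−3)), which is 0.719 and 0.296.

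**4. Observed mortality** = D(1 − fm) / (1 − fDm). Example: D = 2%, f = 1, m = 0.500 gives 0.0100 / 0.9900 = 1.01%.

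| True D | f | L = 30: even, front-loaded | L = 7: even, front-loaded |
|---|---|---|---|
| 0.5% | 1 | 0.25%, 0.14% | 0.44%, 0.35% |
| 2.0% | 1 | 1.01%, 0.57% | 1.77%, 1.42% |
| 2.0% | 0.5 | 1.51%, 1.29% | 1.89%, 1.71% |
| 5.0% | 1 | 2.56%, 1.46% | 4.44%, 3.58% |

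Because D < 1, the ratio (1 − fm)/(1 − fDm) is below 1 whenever fm > 0. The direction of this mechanism therefore does not depend on the assumed timings; only the size does.

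**5. Related-event rate**, true p = 10%, D = 2%, f = 1. If every missed death had a related event, the rate reads (p − Dm)/(1 − Dm); if none did, p/(1 − Dm). Over both death-time shapes this gives 8.7% to 10.1% for L = 30 and 9.5% to 10.1% for L = 7. The shift is small and can go either way. Protocol 10.1 allows retrospective data, so non-fatal events before consent can still be collected in patients who reach consent.

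**6. Would delayed-entry Kaplan-Meier repair it?** Simulated with D = 2% under the same assumptions. The mean returns to about 2.0%, but with consent spread over 30 days only 139 × 1/30 ≈ 5 patients are at risk at day 1 and 14 at day 3. Root mean squared error, in percentage points:

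| N | Consent after surgery | Delayed entry | Crude |
|---|---|---|---|
| 139 | all, 30 days | about 2.6–4.1 | 1.3–1.6 |
| 139 | half, 30 days | 1.4–1.5 | 1.2 |
| 246 | all, 30 days | about 1.9–3.6 | 1.2–1.5 |

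The delayed-entry errors are heavy-tailed and move between simulation runs, so they are given as ranges over runs. At both sizes delayed entry was worse than the crude figure in every scenario tried, including consent over 7 days. It became better in most scenarios only near N = 2,000.

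**7. Precision.** At N = 139, 2% mortality is about 3 deaths; the exact 95% interval for 3/139 is 0.4% to 6.2%. In one small cohort the bias lies within sampling error. It matters most in larger or pooled reports.

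**The case against.** **The base SAP is a template.** SAP 5.1 says that it and its addendum together form the study-specific SAP. The route and the analysis-set details belong in the AP or AD, and SAP 7.9.2 already allows summaries by group where applicable. This stands as a limit: those documents were not available, so no actual cohort can be said to be affected. It does not remove the point, because nothing obliges an addendum to act, and SAP 3 makes the base SAP's method apply to any objective it lists.

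**Early deaths may be captured some other way.** Protocol 8.3 accepts that "Patient or legally authorized representative (LAR) provides authorization and/or consent per institution and geographical requirements", and nothing provides for or expressly bars a representative's authorization after death. Protocol 8.2 mentions an optional tool for tracking enrolment attempts and covers sites where consent is not required; those sites and full-waiver sites might capture early deaths. This stands in part, but the exclusion in Protocol 8.4 of patients inaccessible for follow-up makes capture doubtful even there. A reader might infer that the plan expressly drops deaths before consent. It does not say so; the loss follows from combining its rules, hence 'in effect'.

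**The outcome is minor.** Mortality is secondary and descriptive, with no hypothesis, no performance goal and no planned comparison between cohorts. That is right and limits the weight of the point, but not the need for a correct label.

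**The SAP 6.2 sentence is about product performance.** Its second half does speak of product performance. Its first half describes the sample itself without limit, and for early deaths that is not supported.

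**Conclusion.** The concern holds in limited form. In any cohort, or part of one, consented after the procedure at sites that require consent, mortality counted from the procedure is biased low, and nothing in the two documents requires this to be corrected or disclosed. With a true 30-day mortality of 2.0%, the illustration runs from 1.9%–1.7% (half consented after surgery, over 7 days) to 1.0%–0.6% (all, over 30 days). These sizes rest wholly on the assumed inputs and on this mechanism alone.

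Three stronger readings are not supported:
- That the primary event rate is materially understated: the shift is small and of no fixed direction.
- That the whole registry is affected: cohorts enrolled only before surgery are not.
- That the SAP leaves its population undefined: SAP 5.3 ("enrolled within the enrollment window are eligible to participate in the PSR"), 7.1.1 and 7.1.3 define enrolment and entry to analysis. What is missing is the consequence for mortality.

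This should be fixed in wording and reporting; it does not call for a redesign.

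**What to change.** 1. **SAP 7.9.2, mortality.** Where a cohort includes patients consented after the procedure, label their mortality as conditional on being alive at consent. In mixed cohorts, report it by route beside the pooled figure: before the procedure; after the procedure with consent or data release form; consent waived or not required. Note that the routes may enrol different patients, so the split shows the bias but does not isolate it. Where all patients consent after surgery there is nothing to split and the label does the work.
2. **SAP 7.9.2, Kaplan-Meier.** State the procedure as the time origin and apply the same label. Use delayed entry at the consent date only as a sensitivity analysis in large or pooled reports. State that it assumes consent timing is independent of death risk and cannot recover deaths before the earliest consent.
3. **SAP 6.2.** Delete the representativeness sentence or limit it to the enrolled population.

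**Cost.** Some wording and one extra table. No new data are needed, since Protocol 8.2 already collects the consent date. Intervals widen within strata: from 1.96 × √(0.09/n), a 10% rate has a half-width of 5.0% at n = 139, about 7.0% with two equal strata (n = 70) and about 8.7% with three (n = 46). The pooled figure is still shown.
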